Blood glucose will be monitored weekly at the UTHSC Health Hub months 2 through 4 (e.g., during the Total Diet Replacement phase) and periodically thereafter. Health Coaches and the UTHSC Health Hub medical director should encourage participants to continue any glucose monitoring recommended by their primary care physician or diabetes doctor and to contact their doctor and/or the UTHSC Health Hub Medical Director for blood glucose levels below 70 or above 300. Blood pressure will be monitored weekly at the UTHSC Health Hub for the 2nd – 4th months of the study (e.g., during the Total Diet Replacement phase) and periodically thereafter. Health Coaches and the UTHSC Health Hub medical director should encourage any self-monitoring recommended by their primary care physician. Advise participants to notify their healthcare provider and the Health Hub Medical Director for systolic blood pressure greater than 160 or diastolic BP greater than 100 with symptoms (acute vision changes, headache, chest pain, etc.) or systolic blood pressure greater than 180 or diastolic greater than 110 (regardless of symptoms). Advise participants to immediately call emergency medical services and seek emergent medical care for blood pressure readings 180/110 or higher AND symptoms of chest pain, shortness of breath, numbness, weakness, change in vision, difficulty speaking, or severe headache. In the three months of total diet replacement, participants should be seen at least once a week and should be offered blood glucose and blood pressure checks to assess for hyperglycemia, hypoglycemia, and/or hypertensive episodes. HEAL Diabetes Program Participant Medication Reduction/Discontinuation Instructions will be included in the intervention group's toolkits. Study personnel, including health coaches and the medical director will emphasize instructions for monitoring for adverse events related to blood pressure or blood glucose. Procedures for monitoring blood glucose and blood pressure will be included and further detailed in the Manual of Procedures (MOP).

Adverse events related to medication discontinuation are unlikely but may include hyperglycemia and hypertension. We will monitor those in the intervention group regularly for adverse events related to medication

discontinuation. Adverse event reports related to medication discontinuation may also come from self-reports from at home readings (blood pressure and blood glucose monitoring). Blood pressure and blood glucose screenings should be offered to participants at their weekly health hub visits, as well as through consultation with participants' primary care providers. Regular care providers and participants can call the medical director to report any abnormal or extreme readings that occur outside of health hub's regular monitoring. The health hub medical director and participant will work together to adjust medications based on individual needs and best interests. There is an existing medication reintroduction protocol. However, if a participant does not follow the diet plan which then causes irregular blood pressure or blood sugar, the participant will not be removed from the study. Health hub staff will monitor blood pressure and blood sugar weekly. If a participant needs to increase or reintroduce their medication, the medical director will do that using best judgment and available information.

**C6. Cultural Tailoring.** Because culture plays an integral role in forming individuals' health behaviors and many underserved populations have dietary preferences born from cultural influences and necessity, all component interventions will be extensively culturally tailored. This tailoring will occur during the initial planning phase (see section **D** and **Milestones**) and on an ongoing basis to ensure that they are culturally congruent and appropriate based on the cultural values of the population served. Interventions will be tailored to reflect the subjective culture (i.e., norms and attitudes), behavioral preferences, and expectations of the target population using preliminary focus group data (see section **C2b4**), patient focus groups (three planned in Y1, and two each year in Y2-4), and DWPC Patient and Community Advisory Council focus groups (two total in Y1). We will also employ ongoing interview input from early drop-out, ongoing, and completed participants.

**C7. Intervention Fidelity and Quality Control.** We will focus on design, training, delivery, receipt, and enactment (see analysis section below). To ensure consistency of intervention content and delivery, we will use standardized treatment manuals and procedures. All staff will be thoroughly trained in interventions, and protocol knowledge will be tested among staff. Training will be standardized, tested, and repeated. Even among highly trained staff, slight deviations (intervention drift) from treatment protocol may occur over time. To protect against this, regular "booster" training sessions will be conducted with all members of the study team. The behavioral and HC investigator ([name]) will oversee the fidelity, quality control planning, and implementation of the HC and TM interventions respectively and will conduct intervention meetings bi-monthly and then monthly with staff to discuss difficult cases and help problem solve implementation and participant adherence issues. Fidelity of health coaching to best motivational interviewing practices will be assessed regularly by a member of the Motivational Interviewing Network of Trainers (MINT) using a validated and standardized tool, based on the Motivational Interviewing Treatment Integrity coding system. Health coaches will submit recorded patient sessions (with patient written permission) for coding and assessment bimonthly for their first 6 months of the employment, monthly for two years, and periodically as needed thereafter.

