**C4. Setting.** The city of Memphis is majority African American (63.9%) and low income (average income \$37,199 with 27.8% below the federal poverty level) ranking it as 2nd highest in poverty among the 36 U.S. cities with a population greater than 500,000). The majority of people in Memphis live in HRSA-designated medically underserved and primary care health professional shortage areas (HPSA). Memphis has a very high age-adjusted prevalence of adult obesity at 41.0% and diagnosed diabetes at 15.1% as of 2016. Obesity and diagnosed diabetes rates are even higher among African Americans in Memphis. Thus, this research targets the most vulnerable adult patients with obesity-associated T2D in the U.S.

**C4a. Participant Recruitment Sites.** Potential participants will be recruited with prominently displayed recruitment materials including flyers at the UTHSC Health Hub, the ShelbyCares on 3rd facility, and affiliated clinics. Health hub supervisors will be available to provide study information to potentially eligible patients. Final eligibility will be confirmed following intake completion and subsequent ability to contact patients by phone following intake (Run-in period). All data will be entered into the Research Electronic Data Capture (REDCap) application.

**C4b. Study Population.** Our inclusion and exclusion criteria closely mirror those of the DiRECT study, recruiting adult patients within 6 years of diagnosis of T2D and without serious complications (i.e. recent eGFR  $<30$  mls/min/1.73 m^2) or requiring insulin. All eligible individuals seen in participating locations will be offered participation.

**Inclusion Criteria:** Replicating the inclusion criteria of the DiRECT study, this study includes all persons who meet the following criteria: 1)  $\geq$ 18 years of age, 2) T2D of duration 0–6 years (diagnosis based on 2 recorded A1c tests, self-reported duration of diabetes confirmed by chart review), 3) A1c  $\geq$  6.5% at the screening visit, 4) Body Mass Index (BMI)  $\geq$  30 kg/m^2, 5) receiving care in a clinic the majority of whose adult patients reside in an HPSA, and 6) has a cell phone or smartphone with texting and voicemail capabilities.

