##### **Recruitment Strategy**.

- **Press Release**: A press release describing the study will be approved and distributed through the UTHSC Communications and Marketing department. The press release will be delivered via radio, local television, local newspapers, and local newsletters, as appropriate. The press release will occur at the beginning of recruitment.
- **Social Media Promotion**: Recruitment flyers will be posted on social media sites (i.e., Facebook, Twitter, Instagram)
- **Flyer**: Campaign Flyers will be displayed in various locations interested in participating. The flyers will include the study name, logo, brief description of the study, eligibility bullet points, and contact information including study phone number and website. Community locations are planned to include, but not limited to, the UTHSC Health Hub, churches, community centers, and local businesses. Flyers will be handed out at community events, such as health fairs and church gatherings in catchment areas. Additionally, flyers will be emailed as a PDF attachment interested parties and community organizations' listservs.
- **Word-of-Mouth**: Members of the study team will distribute promotional items and make contact with community members and potential participants. Team members will be responsible for informing all interested persons about the study and as appropriate, provide marketing materials and/or study contact information. Study team members, particularly the RAs, HCAs, and Research Coordinator are expected to maintain good relationships with those involved in recruitment.
- **Refer-a-Friend**: To encourage enrolled participants to inform other interested persons with diabetes about the study, the study team will encourage 'refer-a-friend.'
- **Study Website**: The health hub's website [<https://uthsc.edu/healthhub/>] will have a public page that is devoted to the HEAL Diabetes program and recruitment information. The webpage will include study name, logo, brief description of the study, eligibility inclusion criteria, and directions for interested individuals to contact the study staff.

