Treatment group sessions will begin with an icebreaker to foster authentic relationships and trust, and will focus on goal setting, group problem solving, and preparation for intensive weight loss, and will include interactive education regarding the recommended intensive plant-forward diet including a small cooking demonstration. Treatment group participants will also participate in two individual health coaching sessions and TM in preparation for their “quit date” on which they initiate TDR with whole plant-based foods. All of these sessions will seek to engage both the patient and the person who does the shopping and cooking in the household to obtain buy-in from all family members regarding food replacement plans.

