**C5d. Total Diet Replacement.** Our dietary intervention is based on the successful DiRECT model for TDR adapted to the cultural preferences of our patient population to focus on a whole food plant forward diet consistent with a modified "Daniel Fast" diet. The dietary intervention will be delivered in 3 phases (**Table 2**). In Phase 1 (preparation, 0-1 month) treatment group participants will prepare for TDR as described above. In Phase 2 (TDR, 2-4 months) treatment group participants will receive nutritionally and calorically complete food boxes tailored to participant food preferences sufficient to feed their whole family. Recipes and instructions for serving sizes to provide 800–1200 kcal/d low-glycemic whole food plant forward diet with relatively high protein (25-30%) and < 30% of calories from fat (< 10% from saturated fat) to replace usual foods, with ample fluids (2.25 L) will be included. The total diet replacement (TDR) phase is mostly plant-based, focusing on vegetables

and fruits, but will also include lean meat/protein, eggs, and non-fat or low-fat milk products. Intervention group participants will receive healthy food boxes for 3 months during this time. Grocery supplies will include some foods that can be eaten as snacks and some beverages (i.e. low-fat milk). The nutrition team will estimate energy requirements (within the low calorie diet range) and macronutrients including kilocalories and protein for each individual participant adjusted per equations such as the Institute of Medicines Estimated Energy Requirement (IOM EER) Equations for adults. Nutrition requirements will be adjusted for age, height, weight, level of exercise and presence of any co-morbid conditions. Macronutrients will be distributed accordingly per individual assessment so that despite daily total energy requirement needed to meet the Dietary Reference Intakes for individuals, the meal plans will fall in the lower carbohydrate diet range and higher percentage of total energy requirement from protein and healthy monounsaturated fats to ensure light ketosis. The nutrition team will use a spread sheet to help shoppers then determine total amounts of food needed per box per individual based on individual needs. Participants will be medically monitored by study personnel, including health coaches, nutrition specialists, and the medical director to ensure safe weight loss patterns and behaviors.

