During Phase 2 healthy food boxes (i.e. grocery supplies with recipes) will be delivered to the home on a weekly basis for three months. Preference and special diets will be taken into consideration when putting healthy food boxes together. We will survey participants at baseline with questions about the whole families' food preferences, allergies, and special dietary concerns, like vegan, halal, kosher, etc. Nutritionist [name] will train study personnel to use FARE, an app that will enable us to shop for individuals with identified food allergies as well as specific dietary preferences. Study personnel will be trained to use the app to verify that none of the food box contents include known allergies. Participants will be surveyed at baseline to collect a record of known food allergies/preferences a month before the diet replacement phase. Personnel will also be trained to find an appropriate replacement item without the known allergen. It is free and allows you to pick diet type and then scan an item in the grocery store to ensure it fits a participant's dietary needs. A food delivery service hired by the study who has undergone a background check through the university will deliver food boxes to the participant's home address scheduled at their convenience for 3 months (months 2 through 4). If participants are not at home or are unavailable, it is the assigned study personnel's responsibility to work with the participant to reschedule a delivery and accommodate the participant's schedule to ensure study participants have their weekly food provisions so that they are able to complete all study procedures. While the food boxes contain enough food to feed the whole family, family members should not be treated as study participants. They are not enrolled in the study and have not undergone consent or screening. Study personnel will not perform any study procedures on family. Food boxes are intended to help aid and support the study participant in completing study components.

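### No eligibility rule stops a second member of a treated household from being randomised to control, although the treatment food boxes feed the whole household

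*Combined protocol and SAP*

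**What the plan says.** **Unit of randomisation.** C1a describes individual randomisation of 72 patients. C4d and C8 (Baseline Visit) give 1:1 allocation in blocks of 8. Neither mentions households.

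**Delivery of the diet.** C5d provides treatment participants with food boxes "tailored to participant food preferences sufficient to feed their whole family", brought weekly to the home with recipes for three months. C5a says the treatment group's preparation sessions involve the household's shopper and cook, "to obtain buy-in from all family members regarding food replacement plans". The control diet component in Table 1 is grocery produce vouchers.

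**Recruitment.** Under Refer-a-Friend, C4c aims to "encourage enrolled participants to inform other interested persons with diabetes about the study". C4b adds: "All eligible individuals seen in participating locations will be offered participation".

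**Eligibility.** C4b lists 6 inclusion and 13 exclusion items. None refers to a household, a relative or a shared address. The last exclusion item covers only participation in a different trial.

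**Family members.** C5d states: "While the food boxes contain enough food to feed the whole family, family members should not be treated as study participants". It continues: "They are not enrolled in the study and have not undergone consent or screening". It also says that staff will carry out no study procedures on family.

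**Analysis.** C11 plans intention-to-treat, a repeated-measures mixed model for continuous outcomes and a chi-square test for remission, with no household term. Exposure to the components is recorded from coach attendance logs (Other Factors, after Table 3).

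**The concern.** One treatment component reaches the household, while allocation and analysis are by individual. If a relative of a treated participant is eligible, the plan as written lets that person be randomised, possibly to control, in a home that is receiving the boxes. That control could eat the box food and use the recipes while remaining in the control arm under intention-to-treat. Attendance logs would not show it, so it could not be examined afterwards.

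Two things would be at stake. The first is the treatment contrast, which would most likely move toward no difference. This matters because C4e lists the effect size first among the quantities the pilot will estimate, and section D intends the results to inform larger studies. The second is independence: members of one household share food and habits, and both the chi-square test and the mixed model as described treat them as unrelated.

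**Working it through.** **1. The plan's own figures.** C4e: 8 per month × 9 months = 72; 72 × (1 − 0.15) = 61.2, which matches the stated figure of about 61. The plan gives no power, alpha or effect-size calculation, so there is no such figure to reproduce.

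**2. Does any rule keep relatives out?** The only text that bears on it is the C5d passage on family members. It tells staff how to treat people who eat from the boxes and describes those people as not enrolled. It is not an eligibility criterion, and no screening step in C8 applies it. If a relative did enrol, the bar on study procedures for family could not be kept. The passage therefore shows an intention to keep the two groups apart without putting it into effect.

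**3. Chance that an enrolled pair is split.**
- Same block of 8 (4 per arm): 2 × 4 × 4 / (8 × 7) = 4/7 = 57%.
- Different blocks: 50%.

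Each enrolled household pair thus has a 50-57% chance of placing a control in a home that receives boxes.

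**4. Effect on the weight contrast.** Let k be the number of the 36 controls living with a treated participant, and f the fraction of the treatment benefit that such a control gains. The shrinkage is 10 × f × k/36 kg. Three inputs are assumptions:
- The 10 kg is the loss hypothesised for the intervention in C1c. It is used here as if it were the between-arm contrast.
- f = 0.5 is chosen for illustration.
- k is not given anywhere.

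| k | f = 0.5 | f = 1 (upper bound) |
|---|---|---|
| 0 | 0 kg | 0 kg |
| 1 | 10 × 0.5 × 1/36 = 0.14 kg | 0.28 kg |
| 3 | 10 × 0.5 × 3/36 = 0.42 kg | 0.83 kg |

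**5. How many pairs would that take?** For k = 3, the trial would need 3 ÷ (4/7) = 5.25 to 3 ÷ 0.5 = 6 enrolled pairs, or about 10 to 12 of the 72 participants. For k = 6 it would need 10.5 to 12 pairs, or 21 to 24 participants.

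**6. Remission.** No figure is put on this. Table 3 requires A1c below 6.5% after at least 2 months off diabetes drugs, with two drug classes excepted. Supervised medication discontinuation belongs to the treatment arm only (Table 1, C5g), so sharing food does not carry over the full effect on remission.

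**The case against.** The strongest reply is that C5d already shows the intent: people fed by the boxes are not trial participants. On that view a rule was merely left out of the eligibility list. This is fair as to intent. It does not close the gap, because eligibility and allocation are governed by C4b, C4d and C8, where the rule does not appear.

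The second reply is that the problem may never arise. Both relatives would need type 2 diabetes of at most 6 years, A1c from 6.5% to below 12%, BMI of at least 30, no insulin and at most two hypoglycaemic drugs. The control's follow-up must also overlap the relative's box months. A relative who had already lost more than 5 kg in the previous 6 months would be excluded. All of this stands, and it is why the count may be zero.

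A reader might infer more than the documents support:
- **That a sharing control effectively crosses over.** The boxes are one of seven components. Such a control has no individual energy prescription, coaching, text messages, support groups or supervised medication discontinuation. The serving sizes are set for the participant.
- **That coaching is delivered to the household.** No such component exists. Coaching is individual (C5b), and only the C5a preparation sessions involve the household's shopper and cook.
- **That participants are asked to recruit relatives.** C4c encourages them to inform others, and a friend need not share a home.
- **That the loss is large.** With six controls at full benefit the formula gives 10 × 6/36 = 1.67 kg. That needs 21 to 24 of 72 participants to come from household pairs, which nothing in the documents suggests.

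**Conclusion.** The gap is real but minor. As written, the plan permits a control to live in a home receiving treatment food boxes. Nothing would prevent this or record it, and the likely direction of bias is toward no difference. Its size cannot be established from the documents. Under an assumed 10 kg contrast and half benefit, it runs from nothing to 0.14 kg with one such control and 0.4 kg with three. Full benefit is only an upper bound for weight and is not credible for remission. The independence problem exists for any enrolled household pair, in the same arm or not, but it is not quantified because neither the number of pairs nor their correlation is given. In a 72-patient pilot whose size is described as pragmatic, this is a cheap improvement and does not threaten the design.

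**What to change.** Add an exclusion item to C4b: *a member of the same household has already been randomised in this study*. Check it at screening against the contact details taken then (C8) and the addresses held in the tracking database (C9). Repeat the check immediately before randomisation at the baseline visit, since two relatives could both be screened before either is allocated. Add one sentence to the refer-a-friend text in C4c saying that household members of enrolled participants cannot be randomised but may use the usual Health Hub services.

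The cost is one exclusion line, one screening question and possibly a few lost recruits. C4e expects about 20 eligible patients a month for 8 enrolled, so the target of 72 should not be affected. Provided household membership is correctly identified, the rule removes both within-household sharing and within-household dependence, with no change to the interventions, sample size or analysis.
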